5.3 N/A

5.4 N/A

6.0 Procedures Involved

6.1 This will be a randomized, crossover study designed to differentiate the effects of an acute partial sleep deprivation intervention on markers of central hemodynamics, cardio-autonomic function, physical and cognitive performance, as well as overall health in individuals with high vs low CRF. The study, outlined in Figure 1 and described in detail below, will consist of 5 total visits to the Institute of Sports Sciences and Medicine (ISSM) located on the main campus of Florida State University. On the first visit, participants will report to the ISSM to be informed of the details of the study before giving their oral and written informed consent. Thereafter, participants will be assessed for exercise training status (i.e., trained vs sedentary), body composition, and maximal oxygen consumption capacity (i.e., VO_{2max}). Participants will be dichotomized into one of two test groups – fit or unfit – based on both self-reported training status and VO_{2max} values. The utilization of both training status and VO_{2max} will better allow the selection of individuals with high CRF values not due

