primarily to genotype – a known confounder (41). The American College of Sports Medicine’s classifications of training status (i.e., <150 minutes of moderate-intensity and/or <75 minutes of vigorous aerobic exercise per week for the last 3 months) as well as normative $\text{VO}_{2\text{max}}$ values will be used to dichotomize the groups with the fit (and chronically-trained) and unfit (and sedentary) group having values in the upper and lower quartiles (i.e., $\geq 75^{\text{th}}$ percentile and $\leq 25^{\text{th}}$ percentile) for their age and sex, respectively (42). This equates to a $\text{VO}_{2\text{max}}$ value of ≥ 55.2 and 44.7 ml/kg/min for fit males and females, respectively, and ≤ 40.1 and 30.5 ml/kg/min for unfit males and females, respectively. Participants will then be provided with a wearable, wrist-worn sleep and cardio-autonomic function monitor, to be worn on the non-dominant wrist throughout the entirety of the project timeline, including a two-week initialization period to establish baseline sleep cardio-autonomic data. This initialization period will take place following consent and prior to the first data collection visit. Next, participants will then be familiarized with daily sleep, physical activity, and 3-day nutrition logs as well as a PVT smart phone application, all of which will be performed throughout the study. Lastly, participants will be assessed for sleep chronotype via a morningness-eveningness questionnaire to inform any potential differences in sleep intervention response post hoc. Following the initialization period, participants will be randomly assigned to either a normal or partial sleep deprivation intervention, both of which will last 4 days. The partial sleep deprivation intervention will consist of prescribed bed and wake times eliciting a 30% reduction in habitual time in bed, identical to a protocol utilized by Roberts, et al. (43). Following the first sleep intervention period, participants will again report to the ISSM for the first of four data collection visits (i.e., Post-Test 1). Data collection will consist of assessment of central hemodynamics, cardio-autonomic function, physical and cognitive performance, as well as overall health. Participants will then undergo a 7-day washout/ post-intervention observation period, in which they will continue to track and log their sleep and perform daily PVT to allow for recovery evaluation in those metrics, prior to crossing over to the other sleep intervention. During the washout period, participants will also return to the lab to repeat the blood work and CMJ testing to allow for recovery assessment in those values (i.e., immediate post-intervention vs 3-day post-intervention values; Recovery 1). Following completion of the washout/observation period, participants will crossover to the other sleep intervention and repeat the testing protocols (i.e., Post-Test and Recovery 2). Data collection visits will occur at the same approximate time of day for each individual to account for diurnal patterns in the data collected. In total, the protocol will last approximately 5 weeks and consist of 5 visits.

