VO_{2max} Testing Protocol: Testing will take place on a motorized treadmill (Woodway USA, Waukesha, WI). Oxygen consumption will be measured via a Parvomedics TrueOne 2400 metabolic cart (Salt Lake City, UT). Each testing stage will last for two minutes, and heart rate (HR) and rating of perceived exertion (RPE) will be recorded in the last 15-20" of each stage. The participant will begin at a speed of 3 miles per hour for the warm-up stage. Upon completion of the warm-up the speed will be increased to 5 miles per hour. The speed will be increased by 1.5 miles per hour for each successive stage until an RPE of 13 or greater is achieved. Following this, the speed will remain constant for the remainder of the test. For the following stage, the grade of the treadmill will increase to 2%, and will be increased by an additional 2% for each subsequent stage until volitional exhaustion. Attainment of maximal oxygen consumption will be ensured by satisfying two of three criteria: plateau in oxygen consumption with increasing workload, respiratory exchange rate (RER) >1.1, or RPE >17. Standardized verbal encouragement will be provided throughout the test. Immediately after the test, participants will be given a three-minute cooldown period in which they will be asked to walk at 3 mph.

Sleep Intervention: Following the two-week initialization period, participants will be randomly assigned to either a normal or partial sleep deprivation intervention, both of which will last 4 days. The last week of the two-week initialization period will be used to

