Experimental Visits: Following the first sleep intervention period, participants will come in for the first of four data collection visits (i.e., Post-Test 1). Data collection visits will begin of the completion of the Pittsburgh Sleep Quality Index (PSQI) and Profile of Mood States (POMS) questionnaire to characterize sleep quality and psychological mood states, respectively. Next, central arterial pulse wave form analysis and pulse transit time (carotid-femoral PWV [cf-PWV]; via applanation tonometry) will be assessed using a SphygmoCor XCEL device (AtCor Medical, New South Wales, Australia), followed by a standard venipuncture procedure to allow for inflammatory marker characterization, total blood cell counting, as well as blood lipid and glucose profiling to account for known hemodynamic confounders (26). The venipuncture procedure will be performed by the primary investigator (certified phlebotomist trained; 5+ years of experience) following the attached standard operating procedure for venipuncture and will entail the collection of 10-30 mL of blood, as is typical of a standard blood venipuncture procedure. If the primary investigator is unavailable to perform the procedure or is unable to do so, the Clinical Research and Trials Unit will be utilized. Lastly, participants will perform a short countermovement jump (CMJ) test to quantify their reactive strength index (RSI).

Participants will then undergo a 7-day washout/ post-intervention observation period, in which they will continue to track and log their sleep and perform daily PVT to allow for recovery evaluation in those metrics, prior to crossing over to the other sleep intervention. During the washout period, participants will also return to the lab to repeat the blood work and CMJ testing to allow for recovery assessment in those values (i.e., immediate post-intervention vs 3-day post-intervention values; Recovery 1). Following completion of the washout/observation period, participants will be assigned to the other sleep intervention in a crossover fashion and complete the second 4-day intervention before returning for another data collection visit (i.e., Post Test 2) identical to Post Test 1. They will then enter another 7-day post-intervention observation period and performing a second recovery data collection visit (i.e., Recovery 2). Data collection visits will occur at the same

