16.2 N/A

17.0 Data Management and Confidentiality

17.1

Sample Size Estimation

Sample size requirements were determined via a priori power analyses using G*Power software (Ver. 3.1.9.4; Heinrich-Heine-Universität Düsseldorf, Düsseldorf, Germany) to ensure sufficient statistical power. To inform the expected effect size, we referenced Sunbul, et al. (49) who reported significantly higher wave velocity (PWV) values (5.33 ± 0.46 m/s) following one night of total sleep deprivation compared to one night of normal sleep (5.15 ± 0.26 m/s; $p=0.001$) in young, healthy males and females. Acknowledging that this will consist of an acute partial sleep deprivation intervention, a Cohen's f value of 0.24 was used in conjunction with an α level of 0.05, power of 0.80, with 2 groups (crossover design; 4 measures each), and a conservative correlation among repeated measured of 0.5. This resulted in a sample size estimate of 24 participants. The planned sample size was then increased based on the differences between the current study, the previous work, and the assessment of several secondary outcomes, as well as to account for expected attrition (~20%). Therefore, 30 participants will be recruited to maximize statistical power and account for expected attrition.

Statistics

Data will be presented as means \pm SD if normally distributed and assessed for normality via a Shapiro-Wilk Test. Assuming normality, all variables will undergo null-hypothesis testing with the α level set to 0.05. In the case that normality is violated, the appropriate non-parametric alternatives will be utilized. Analyses will be conducted using SPSS version 29.0 (SPSS, Inc., Chicago, IL).

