Analysis of Variance: Central hemodynamic and arterial stiffness variables will be interpreted using a mixed-model (i.e., within-between) repeated measures analysis of variance (RMANOVA) to identify interactions between multiple groups and conditions. Specifically, to test the hypothesis that individuals with higher CRF would demonstrate a blunted arterial stiffness response (i.e., maintained pulse transit times) to the acute partial sleep deprivation intervention, cf-PWV will be assessed following 4 consecutive nights of both normal sleep and restricted sleep and compared between the two groups. Likewise, all secondary variables will be assessed at pre-specified time points using a within-between interaction RMANOVA to test the hypotheses that individuals with higher CRF would demonstrate a blunted effect of partial sleep deprivation on markers of physical and cognitive performance (i.e., maintained RSI and PVT, respectively) as well as on markers of overall health (i.e., maintained cardio-autonomic function parameters, pro- and anti-inflammatory serum cytokine levels, and mood states).

In the case that sphericity is violated, a Greenhouse-Geisser correction will be performed. In the case of significance, a post hoc one-way ANOVA with Bonferroni tests will be used to identify significant differences. Effect sizes (ES) will be calculated by standardizing mean differences to the standard deviations (SD) of the placebo condition. Effect sizes will be qualified as follows: small $d = 0.2$, moderate $d = 0.5$, and large $d \geq 0.8$ (50).

17.2 The data will be kept secure through several routes. First, only the CITI certified research team will be allowed to be involved in the data collection process. Further, after acute bouts of data collection occur, all data will be collected together by the PI. If the data is physical, it will be kept in a locked drawer, behind a locked laboratory door. If the data is electronic, it will be kept on a password secured computer that only the PI may gain access. All human data will be coded, such that without the code it becomes unidentifiable.

17.3 Quality control of collected data will be ensured by controlling as many external variables as is reasonable. Further, biological measures (primary outcomes) will be measured in duplicate with the average of each measure used in the final assessment.

17.4 Describe how data or specimens will be handled study-wide:

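### No balancing of intervention order within the fit and unfit groups is specified and the RMANOVA has no period term, so any period effect costs precision on the group-by-condition interaction

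*Combined protocol and SAP*

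**What the plan says.** Fitness group is an observed classification made at the first visit: "Participants will be dichotomized into one of two test groups" (Section 6.1). Order comes later, after the two-week initialization period: "participants will be randomly assigned to either a normal or partial sleep deprivation intervention, both of which will last 4 days" (Section 6.2, Sleep Intervention). Sections 6.1 and 6.2 give no allocation ratio, block size, stratification factor or rule for balancing order.

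Between the two conditions, "Participants will then undergo a 7-day washout/ post-intervention observation period" (Section 6.1), and then "participants will be assigned to the other sleep intervention in a crossover fashion" (Section 6.2, Experimental Visits). Visits are held at about the same time of day for each person.

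Section 17.1 analyses the hemodynamic variables with a within-between "repeated measures analysis of variance (RMANOVA) to identify interactions between multiple groups and conditions". For the primary arterial stiffness hypothesis, "cf-PWV will be assessed following 4 consecutive nights of both normal sleep and restricted sleep and compared between the two groups". No period, sequence or order term is named there or elsewhere.

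**The concern.** The trial's key contrast is whether the restricted-minus-normal difference in cf-PWV is smaller in fit than in unfit participants. In a two-period crossover, anything that changes between the first and second post-test enters each person's difference, with a sign set by the order received. If the model has no period term, that variation is counted as random error. If the fit and unfit groups also have different order splits, part of the period effect appears as a difference between fitness groups.

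The washout and the fixed time of day deal with carryover and diurnal variation. Neither removes a period effect. For cf-PWV the plausible source is growing familiarity with tonometry. Post-Test 1 is the first tonometry session that Section 6.2 describes, and the visit 1 familiarisation covers only the logs and the PVT application.

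**Working it through.** **The plan's own figure.** Section 17.1 states that a Cohen's "f value of 0.24 was used in conjunction with an α level of 0.05, power of 0.80", with 2 groups and "4 measures each), and a conservative correlation among repeated measured of 0.5". From the cited PWV values, the pooled SD is √((0.46² + 0.26²)/2) = 0.374, so d = 0.18/0.374 = 0.48 and f = d/2 = 0.24. For the within-between interaction, λ = f²·N·m/(1 − ρ) = 0.0576 × 24 × 4/0.5 = 11.06 on 3 and 66 df, which gives power 0.780. The smallest even N reaching 0.80 is 26 (power 0.817), and f = 0.25 gives exactly 24. The stated 24 is therefore reproduced to within two participants, and 24/0.8 = 30. Nothing in this calculation allows for a period effect.

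**Inputs for the check**
- 15 fit and 15 unfit completers: assumed as an equal split of the planned 30.
- SD of D, the restricted-minus-normal difference: √(0.46² + 0.26² − 2 × 0.5 × 0.46 × 0.26) = √0.1596 = 0.40 m/s, from the cited SDs and the plan's correlation of 0.5.
- Group difference in D: 0.40 m/s, assumed. The documents give none.
- Period effect P, second period minus first: not in the documents. Shown at 0, 0.09, 0.18 and 0.36 m/s. The cited sleep-deprivation effect is 5.33 − 5.15 = 0.18, so these are none, half, all and twice that effect.

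**Mechanism.** With two conditions, the interaction test equals a two-sample t test on D. P adds +P to D for a person given restricted sleep second and −P for one given it first. If q is a group's share given restricted sleep second, its mean D moves by P(2q − 1). The interaction therefore moves by 2P(q_fit − q_unfit). Under simple randomisation the expected value of that shift is zero, and the variance of D rises from 0.1596 to 0.1596 + P².

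**Power.** Without the term, the noncentrality is 0.40/(SD × √(2/15)) on 28 df. At P = 0 this is 0.40/(0.3995 × 0.3651) = 2.74, giving power 0.75. Simulation under simple randomisation agrees to within about a point:

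| P (m/s) | SD of D, no period term | Power without term | Power with term |
|---|---|---|---|
| 0 | 0.40 | 0.75 | 0.74 |
| 0.09 | 0.41 | 0.73 | 0.74 |
| 0.18 | 0.44 | 0.67 | 0.74 |
| 0.36 | 0.54 | 0.50 | 0.74 |

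Overall type I error stays about 0.05 in every row, with or without the term.

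**Chance imbalance of order.** With two independent Binomial(15, 0.5) counts, the number given a particular order first differs between groups by at least 1 with probability 86%, by 3 or more with 36%, and by 5 or more with 10%. Balancing order over all 30 but not within group raises the last two to 47% and 14%.

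**Effect of a given split.** At 10/15 versus 5/15 with P = 0.18, the shift is 2 × 0.18 × 5/15 = 0.12 m/s, and type I error conditional on that split is about 9%. When the counts differ by 2, conditional type I error at P = 0.18 is about 4%, below nominal, because the inflated residual outweighs the small shift.

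**Why both parts of the fix are needed.** Take P at half the SD of D (about 0.20 m/s) and an interaction powered at 0.80 with no period effect. Stratified order without a period term gives power 0.72 and type I error 0.029. A period term with simple randomisation gives 0.78. Both together give 0.80 and about 0.05.

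**The case against.** The case against has five parts.

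- **Silence on stratification.** The documents do not say that order ignores fitness group. Group is known in time, so stratified order is possible under the plan. This stands: the gap is that balancing is not specified, not that it is ruled out.
- **False positives.** A reader might infer that the missing term biases the interaction or inflates its type I error. The plan's random order does not support that. Expected bias is zero and overall type I error is about 5%. The 9% figure is conditional on a split whose counts differ by 5, and differences that large or larger arise about one time in ten.
- **Size of P.** A period drift of 0.18 m/s equals the whole effect of a night of total sleep deprivation in the cited study. At 0.09 m/s the term gains about a point, and at zero it costs one. This also stands, and is why the full range is shown.
- **Evidence for a period effect.** Practice on the PVT, venipuncture and jumping do not bear on cf-PWV, and the PVT is done daily from enrolment, so much of its practice comes before the first period. Starting the second intervention 11 days after the first (4 + 7) changes weekdays, but this is a common period effect only if everyone starts on the same weekday, which the plan does not require. Only tonometry familiarity bears on the primary outcome, and the documents give no data on it.
- **Standard deviation.** Using the pooled 0.374 as the SD of the difference gives more power in every scenario. The unpooled 0.40 follows from the two cited SDs and is used here. The pattern is the same with either.

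None of this removes the omission or the algebra. It limits the claim to precision, and to the one order split that the trial will actually have.

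**Conclusion.** The plan specifies neither balance of order within fitness group nor a period term, and both omissions bear on its key interaction. That part is certain from the text. The size is not. Under the assumptions above, the power lost by leaving out the term is about 1 point at P = 0.09, 7 points at 0.18 and 24 points at 0.36 m/s, and nothing is lost if there is no period effect. In addition, there is a 36% chance under simple randomisation that order counts differ between groups by 3 or more of 15. In that case the interaction moves by at least 2P × 3/15 = 0.4P, in a direction that cannot be known in advance.

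The results rest on 15 completers per group, an SD of 0.40 m/s, an assumed 0.40 m/s group difference and a period effect common to both groups. This is an inexpensive precision safeguard that should be adopted. It is not a flaw that invalidates the test.

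**What to change.** - **Randomisation:** generate order in permuted blocks from separate lists for the fit and unfit groups. Near-equal order within each group also keeps a period effect that differs by fitness almost entirely out of the contrast.
- **Model:** in Section 17.1, specify a linear mixed model with fixed group, condition, period and group-by-condition terms and a random participant effect. Equivalently, regress each person's restricted-minus-normal difference on group and order. Use the same structure for the secondary outcomes, where practice effects are more plausible.
- **Reporting:** give the order split by fitness group, as randomised and as analysed. Attrition of about 20% (Section 17.1) and withdrawal for non-compliance (Section 14.1) can unbalance order after randomisation, so stratified lists alone are not enough.

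The cost is two lists instead of one and 1 degree of freedom. If there is no period effect, the term costs about 1 to 2 power points under simple randomisation and almost nothing once order is stratified. No visits, procedures or participants are added. The change should be written into the plan before order is assigned and outcome data are seen.

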characterize typical sleep duration (i.e., total sleep time, total time in bed, and typical bed/wake times [values not dependent on initialization of WHOOP device]). During the normal sleep intervention, participants will be prescribed bed and wake times consistent with those observed to ensure the maintenance of typical sleep. The partial sleep deprivation intervention, conversely, will consist of prescribed bed and wake times eliciting a 30% reduction in habitual time in bed, identical to a protocol utilized by Roberts, et al. (43). Specifically, wake times will be individualized to the participant's typical sleep habits determined previously, while delayed bed times will be prescribed to achieve the 30%-time reduction. Administration of the partial sleep deprivation intervention in this manner will allow for consistent time intervals between waking and data collection between both sleep interventions, thus mitigating the effects of diurnal patterns altered by intervention. Intervention compliance will be monitored via use of the sleep data collected with the WHOOP bands as well as the daily sleep logs. Those who deviate from the prescribed in-bed and out-of-bed times by more than 30 mins will be asked to restart the intervention. During both interventions, participants will be asked to maintain typical physical activity, including the timing of said activity, and eating habits as well as complete the physical activity and nutrition logs to characterize those lifestyle habits.

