9.0 Study Timelines

9.1 *Describe:*

- The duration of an individual subject's participation in the study is ~1.5 months (~35 days).
- The duration anticipated to enroll all study subjects is 18 weeks.
- The estimated date for the investigators to complete this study (complete primary analyses) is December 2025.

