14.0 Withdrawal of Subjects

- 14.1* Subjects will be withdrawn from the research without their consent if they do not comply with prescribed bed and wake times for the entirety of either intervention.
- 14.2* Upon discovering the adherence problem, participants will be contacted via telephone or face-to-face and politely told they are disqualified from continuing the study due to adherence.
- 14.3* If participants withdraw of their own volition or are withdrawn by the PI, the research team will notify them via phone call or word of mouth in person. All data collected up until the point of withdrawal may be used at the PI's discretion for the results.

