19.0 Provisions to Protect the Privacy Interests of Subjects

19.1 Only the research team will have access to personal information. Furthermore, it will be coded to protect participant privacy.

19.2 The research team will be kind, gentle, and explain every step of the research protocol to the participant prior to conducting each test of the experiment. Together, these conversations and familiarizations, paired with a friendly demeanor, will promote the participants of the study feeling at ease.

19.3 The research team may only access personal information about participant's by going through the PI. The PI is the only person who has access to the password protected computer and key to the locked drawer. The password and key will not be given out, ensuring the bottleneck of information going through the CITI trained PI.

Further, the data collected via the WHOOP and Sway Medical app will be provided, by the participant, to the PI for analysis of the data needed for study participation.

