22.0 Consent Process

22.1 Indicate whether you will you be obtaining consent, and if so describe:

- Consent will take place within the ISSM research laboratory.
- The prospective participant may take as long as they would care to between being informed and signing the informed consent. This is completely up to their discretion.
- Ongoing consent will be ensured via weekly check-ins with regard to their adherence to the supplementation protocol.
- Yes, we will follow “SOP: Informed Consent Process for Research (HRP-090).”
 - Only the trained PI or a co-investigator will be permitted to lead the informed consent process with the potential participant.
 - The discussion of informed consent will take as long as is needed for the potential participant to feel informed and comfortable about their voluntary participation in this research.
 - We will emphasize that this is completely voluntary and that the participant is able to refuse or withdraw from the study at any time.
 - To ensure the subjects’ understanding, we will ask the participants to repeat back to us the perceived risks and benefits.
 - The informed consent document will be at a 10th grade reading level, however as previously mentioned all topics will be read to the participants and explained.

Non-English Speaking Subjects

- There are no current indications that our subjects will not speak English. If a potential participant would like to take part in the study and meets the inclusion criteria appropriate accommodations will be made to ensure their consent is informed in their language. Accommodations will include a non-English consent form.
- N/A
- N/A

Waiver or Alteration of Consent Process (consent will not be obtained, required information will not be disclosed, or the research involves deception)

- Review the “CHECKLIST: Waiver or Alteration of Consent Process (HRP-410)” to ensure you have provided sufficient information for the IRB to make these determinations.

Subjects who are not yet adults (infants, children, teenagers)

- N/A

Cognitively Impaired Adults

- N/A

Adults Unable to Consent

- N/A

Adults Unable to Consent

- N/A

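### Section 14.3 leaves use of withdrawn participants' data to discretion and no analysis set is defined, so inclusion in the primary test could be settled after results are seen

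*Combined protocol and SAP*

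**What the plan says.** Section 6.2 (Sleep Intervention) sets the restricted condition as "prescribed bed and wake times eliciting a 30% reduction in habitual time in bed", for 4 days. It monitors compliance through the wearable and daily sleep logs, and then states: "Those who deviate from the prescribed in-bed and out-of-bed times by more than 30 mins will be asked to restart the intervention". It gives no interval before the restart, no maximum number of restarts, and no rule for nights already completed. The only recovery interval in the document is the 7-day washout that follows a completed intervention.

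Section 14.1 withdraws participants "if they do not comply with prescribed bed and wake times for the entirety of either intervention". Section 14.3 then says: "All data collected up until the point of withdrawal may be used at the PI's discretion for the results".

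Section 17.1 describes the primary comparison: "cf-PWV will be assessed following 4 consecutive nights of both normal sleep and restricted sleep and compared between the two groups". The method is a within-between repeated measures ANOVA. The section names no analysis set, no handling of incomplete crossovers and no treatment of restarted periods.

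**The concern.** Section 14.3 is not mere silence. It is an explicit permission to decide, case by case, whose data count, and nothing in section 17.1 overrides it. The primary test is small (30 participants, two groups), so adding or removing a few people can move a p-value across 0.05. If that choice is open once the cf-PWV results are known, the nominal 5% level no longer holds.

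The reach is limited. A repeated measures ANOVA on the two post-tests drops anyone lacking one of them, so discretion affects the primary test only for participants who have both and are then withdrawn.

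The restart rule raises a separate, smaller question. Compliant restricted nights served before a failed night could add to the four that the test is defined on, so cumulative sleep loss could vary among restarters.

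**Working it through.** **Inputs from the plan.** Section 17.1: PWV 5.33 (SD 0.46) against 5.15 (SD 0.26) m/s, correlation 0.5, α 0.05. Sections 1.0 and 12.1: 30 participants. Sections 6.1 and 6.2: 14-day initialization, 4-day interventions, 7-day washout and 7-day final observation. **Assumed:** 15 per group; numbers flagged; timing of restarts; habitual time in bed.

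**Plan's own figure.** d = 0.18 / √[(0.46² + 0.26²)/2] = 0.18/0.374 = 0.48, and f = d/2 = 0.24, as stated. The point does not depend on the sample size.

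**Discretion.** With two conditions, the group-by-condition test equals a two-sample t-test on within-person differences. Null trials were simulated with 15 per group and m participants with both post-tests flagged at random. The smallest p-value among the permitted analyses was reported.

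| Flagged (m of 30) | Fixed rule | Keep all or drop all | Choice per participant |
|---|---|---|---|
| 1 | about 5% | 5.9% | 5.9% |
| 3 | about 5% | 6.5% | 8.1% |
| 6 | about 5% | 7.1% | 13% |

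Repeat runs agree to within about 0.2 percentage points. For m = 1 the two kinds of choice are the same. Either fixed rule alone gave 4.9% to 5.0%.

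**Restarts.** If a restricted-sleep restart is immediate after failure on night k, compliant restricted nights before the post-test are (k − 1) + 4, that is 4, 5, 6 or 7 for k = 1 to 4. At an assumed 8 h in bed each night costs 0.30 × 8 = 2.4 h, so the extra is 0, 2.4, 4.8 or 7.2 h over the planned 4 × 2.4 = 9.6 h. The maximum extra is 6.3 h at 7 h in bed and 8.1 h at 9 h. The failed night is not counted and may give sleep back, so these are not net doses.

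**One scenario for the effect of restarts (not a bound).** Assume a linear effect of 0.18 m/s per 4 nights, with 3 of 15 in one group only having 3 extra nights.

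- Shift = (0.18/4) × 3 × 3/15 = 0.027 m/s.
- SD of the within-person difference = √(0.46² + 0.26² − 2 × 0.5 × 0.46 × 0.26) = 0.399.
- SE of the group difference = 0.399 × √(2/15) = 0.146.
- The shift is 0.185 SE, and rejection under the null is 5.4%.
- If restarts are balanced between groups, the shift is 0 and variance rises by (0.135² × 0.2 × 0.8)/0.399² = 1.8%.

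**Schedule.** 14 + 4 + 7 + 4 + 7 = 36 days. One restart after a 7-day break adds k + 7 = 8 to 11 days, giving 44 to 47.

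**The case against.** The best defence is that the discretion bites only after a chain of events: a participant deviates, is not caught during a monitored 4-night period, completes both post-tests, and is withdrawn afterwards. A restart rule makes most sense if adherence is checked before the post-test. This stands as a limit on how often the problem arises, and no frequency can be given. It does not remove the permission in 14.3, and no stated review schedule rules the chain out.

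A reader might go further and infer that late discovery is likely, because section 19.0 says "the data collected via the WHOOP and Sway Medical app will be provided, by the participant, to the PI for analysis" and the only adherence contact with a stated frequency is in section 22.0: "Ongoing consent will be ensured via weekly check-ins with regard to their adherence to the supplementation protocol". The documents do not support that. The first is a privacy provision about who supplies app data, not when adherence is reviewed. The second is a consent provision naming an intervention this study does not have, and is poor evidence of the sleep-monitoring schedule.

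A reader might also infer that 6.2 and 14.1 contradict each other. They need not: restart first, then withdrawal if compliance still fails, is the natural reading.

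On restarts, it is fair to say that the prescription itself (30%, 4 days) is fixed, that any completed restart still delivers four consecutive restricted nights, and that section 6.2 does not say the restart is immediate. All of that stands, which is why restarts are secondary here.

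**Conclusion.** The concern holds, as a minor one. Section 14.3 with no analysis set in 17.1 leaves inclusion in the primary test open for participants withdrawn for non-adherence after both post-tests. If 1 to 6 of 30 were in that position, type I error would be roughly 6% to 7% under an all-or-none choice and 6% to 13% under individual choice, against 5%. These figures assume that flagging is unrelated to outcome and that the most favourable analysis is always reported. The number flagged is an assumption throughout.

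The restart gap is an operational omission with little shown effect. A reader might infer that it biases the comparison of fit and unfit groups. Nothing in the documents shows that restarts would differ by group, and the one unbalanced scenario worked above moves the rejection rate only to 5.4%.

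**What to change.** 1. Replace the discretion in 14.3 with an inclusion rule fixed before data are seen, and repeat it in 17.1. For example, all participants with post-test data form the primary set, and those adherent under the 30-minute rule form a sensitivity analysis. The reverse is equally valid if fixed in advance.
2. State that wearable and log data are checked before each post-test, so that non-adherence is found before outcomes exist.
3. For the restricted condition only, allow one restart, begun after 7 days of habitual sleep (the washout length already in section 6.2). A normal-sleep restart adds no restricted nights and needs no such wait.
4. Optional: a linear mixed model with group, condition, their interaction, period and a random participant effect. It keeps participants with one period only. The gain is modest: with 1, 2 or 3 such participants per group, the interaction variance falls by about 1.8%, 3.7% or 5.9%.

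The cost is a few protocol sentences, one sensitivity analysis and a data check before each post-test. No added participants or equipment are needed. One restricted-sleep restart takes a participant to 44 to 47 days. Section 9.0 reads "participation in the study is ~1.5 months (~35 days"; the 1.5 months roughly covers this, but the 35-day figure and the five-week figure in sections 6.1 and 6.2 need updating. Anyone withdrawn before a post-test still contributes no cf-PWV value.
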